4.2 SCIENTIFIC RATIONALE FOR STUDY DESIGN

The study design of this trial using the IBSM model has been used previously to safely and effectively determine the PK/PD relationship of several antimalarial agents [6-9]. The *P. falciparum* 3D7 challenge agent used to initiate blood-stage malaria infection in this study has been well characterised, with consistent and reproducible parasite growth occurring following intravenous inoculation of healthy participants in previous studies. Experience from these studies indicates that parasitaemia will be above 5,000 parasites/mL on Day 8 following inoculation, but clinical symptoms of malaria will either be absent or only mild in severity.

The duration of confinement within the clinic following dosing with pyronaridine on Day 8 (96 hours) is considered appropriate to ensure close monitoring of participants for safety purposes and to enable frequent blood sampling for parasitaemia and drug concentration measurements. Blood sampling time points have been selected by taking into account data from previous clinical PK studies, as well as

preclinical data on the antimalarial activity of pyronaridine. These time points may be adjusted during the study, by means of a protocol amendment, based on the emerging data in order to optimally determine the exposure/response relationship of pyronaridine.

The total follow-up period following pyronaridine dosing (42 ± 2 days) is equal to three times the elimination half-life of pyronaridine (approximately 14 days). This duration was selected to allow sufficient time for pyronaridine blood concentrations to fall to a level amenable to parasite regrowth, which is required to calculate the PK/PD parameters. Further, this duration will ensure that participants have a negligible blood concentration of the IMP at the completion of the study.

Compulsory treatment with the registered antimalarial Riamet® (artemether/lumefantrine) will occur for all participants to ensure all parasites are cleared at the completion of the study. *P. falciparum* 3D7 parasites are known to be sensitive to artemether/lumefantrine, and Riamet® has been effective in clearing parasitaemia in previous IBSM studies using this challenge agent. A single dose of Primac® will be used to ensure clearance of gametocytes (the life cycle stage responsible for transmission to mosquitoes) if these are present at any time point after the confinement period at the Investigator's discretion. An alternate registered antimalarial treatment Malarone® (atovaquone/proguanil) will be used in the event of contraindication to Riamet®. Malarone has also previously been effective in clearing *P. falciparum* 3D7 parasitaemia [22]. If in the rare event participants are unable to complete oral antimalarial rescue treatment, they will be admitted to hospital to receive intravenous artesunate, the recommended parenteral treatment of malaria in Australia.

4.3 JUSTIFICATION FOR DOSE

Pyronaridine will be administered as a single oral dose on Day 8, with different doses to be tested across and within cohorts in order to effectively characterise the PK/PD relationship. Each cohort will comprise up to three dose groups, with participants randomised to a dose group on the day of dosing. For each cohort, the SDRT will meet between Day 0 and Day 8, to decide on the dose/s to be administered. Dose selection will be decided based on number of participants inoculated with the malaria challenge agent, and when applicable available data from previous cohorts.

The highest dose of pyronaridine administered will be no more than 720 mg. This dose is equal to the maximum single daily dose of pyronaridine administered to adult patients ≥ 65 kg treated with Pyramax® (pyronaridine/artesunate combination) in accordance with manufacturer's product information for the treatment of acute uncomplicated malaria. Pyramax® is administered as a multiple dose treatment course (daily dosing with 720 mg pyronaridine/ 240 mg artesunate over three days for adults ≥ 65 kg), thus the total exposure to pyronaridine following administration of a single dose of 720 mg in the current study is expected to be lower than occurs during a course of Pyramax® treatment. A dose of 720 mg may be required to determine the maximum killing rate (E_{max}) of pyronaridine in the IBSM model.

The lowest dose of pyronaridine administered in this study will be no less than 180 mg. Modelling studies using clinical PK data and preclinical PD data (*in vitro* and murine studies) have indicated that a dose as low as 180 mg may be required for parasite regrowth to occur following initial parasite clearance. Parasite regrowth is required in this study to calculate all PK/PD parameters (primary endpoint).

4.4 END OF STUDY DEFINITION

A participant is considered to have completed the trial if they have completed all phases of the trial including the last visit or the last scheduled procedure shown in the Schedule of Activities (SoA), Section 1.4. For the purposes of clarity, a participant may still be considered to have completed the trial if they have not completed all scheduled procedures. The end of the trial globally is defined as the time at which all participants have completed the trial

5 STUDY POPULATION

5.1 INCLUSION CRITERIA

Individuals must fulfil all of the following criteria to be eligible for inclusion in this trial:

Demography

1. Male or female (non-pregnant, non-lactating) aged 18 to 55 years inclusive who will be contactable and available for the duration of the trial and up to two weeks following the EOS visit.
2. Total body weight greater than or equal to 50 kg, and a body mass index (BMI) within the range of 18 to 32 kg/m² (inclusive). BMI is an estimate of body weight adjusted for height. It is calculated by dividing the weight in kilograms by the square of the height in metres.

Health status

3. Certified as healthy by a comprehensive clinical assessment (detailed medical history and full physical examination).
4. Fully vaccinated (meaning first, second and booster dose) against COVID-19 within 14 days of planned inoculation date.
5. Vital signs at screening (measured after 5 min in the supine position):
 - Systolic blood pressure (SBP) - 90–140 mmHg,
 - Diastolic blood pressure (DBP) - 40–90 mmHg,
 - Heart rate (HR) 40–100 bpm.
6. At Screening and pre-inoculation with the malaria challenge agent: normal standard mean of triplicate 12-lead electrocardiogram (ECG) parameters after 5 minutes resting in supine position in the following ranges:
 - a. *QTcF ≤450 msec (male participants); QTcF ≤470 msec (female participants);*
 - b. *QRS 50–120 msec*
 - c. *PR interval ≤ 210 msec for both males and females, and*
 - d. *Normal ECG tracing unless the PI or delegate considers an ECG tracing abnormality to be not clinically relevant.*
7. Women of childbearing potential (WOCBP) who anticipate being sexually active with a male during the trial must agree to the use of a highly effective method of birth control (see below) combined with a barrier contraceptive from the screening visit until 100 days after the last dose of pyronaridine (covering a full menstrual cycle of 30 days starting after 5 half-lives of last dose pyronaridine) and have a negative result on urine pregnancy test performed before inoculation with the malaria challenge agent.

Note:

- a. Highly effective birth control methods include: combined (oestrogen and progestogen containing) oral/intravaginal/transdermal/implantable hormonal contraception associated with inhibition of ovulation, progestogen-only oral/injectable/implantable hormonal contraception associated with inhibition of ovulation, intrauterine device, intrauterine hormone-releasing system, bilateral tubal occlusion, vasectomised partner, or sexual abstinence or same sex relationship.*
 - b. Female participants who are abstinent (from penile-vaginal intercourse) must agree to start a double method if they start a sexual relationship with a male during the study. Female participants must not be planning in vitro fertilisation within the required contraception period.*

8. Women of non-childbearing potential (WONCBP) are defined as:

- a. Natural (spontaneous) post-menopausal defined as being amenorrhoeic for at least 12 months without an alternative medical cause with a screening follicle stimulating hormone level (FSH) >25 IU/L (or at the local laboratory levels for post-menopause)*
 - b. Premenopausal with irreversible surgical sterilization by hysterectomy and/or bilateral oophorectomy or salpingectomy at least 6 months before screening (as determined by participant medical history)*
9. Males who have, or may have, female sexual partners of child bearing potential during the course of the study must agree to use a double method of contraception including condom plus diaphragm, or condom plus intrauterine device, or condom plus stable oral/transdermal/injectable/implantable hormonal contraceptive by the female partner, from the time of informed consent through to 70 days (covering a spermatogenesis cycle) after pyronaridine administration. Abstinent males must agree to start a double method if they begin sexual relationship with a female during the study and up to 70 days after the last dose of pyronaridine. Males with female partners of child-bearing potential that are surgically sterile, or males who have undergone sterilisation and have had testing to confirm the success of the sterilisation, may also be included and will not be required to use above described methods of contraception.

Regulations

10. Completion of the written informed consent process prior to undertaking any trial-related procedure.
11. Must be willing and able to communicate and participate in the whole trial.
12. Agreement to adhere to Lifestyle Considerations (see Section 5.3) throughout trial duration
13. Agreement to provide current contact details (two telephone numbers including a mobile number and a responsible adult as an emergency contact) and a relevant email address.

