1.2 SCHEMA

1.3 SCHEDULE OF ACTIVITIES

The below table summarises the activities and procedures to be conducted as per this protocol during screening, eligibility, malaria inoculation, out patient monitoring, confinement, and at the end of study. This is a summary only, Section 8.1 provides detailed information about the assessments required at each time-point. There may be multiple samples/assessments for some activities on a particular day. Sections 8.2-8.3 provide more information about how to perform the assessments.

	Screening	Eligibility ^a	Malaria inoculation	Phone contact	Malaria monitoring ^b	IMP administration and clinical unit confinement ^c					Out-patient monitoring ^d	EOS
Day	-28 to -1	-3 to -1	0	1 to 3	4 to 7	8	9	10	11	12	13 to 50±2	50±2
Eligibility assessments												
Informed consent	X											
Beck Depression Inventory-II	X											
Cardiovascular risk	X											
Demography	X											
Medical and social history, inc/exc. criteria, & prior medications	X		X									
Drug & alcohol screen	X		X			X						
Body height	X											
Body weight	X											X
Serology & RBC alloantibody	X											X
Coagulation profile	X											
COVID-19 testing ^l		X	X			X (D 6 am)	X					
G6PD	X											
Serum pregnancy test (all females at screening & WOCBP at EOS)	X											X
Urine pregnancy test (WOCBP)			X				X					

	Screening	Eligibility ^a	Malaria inoculation	Phone contact	Malaria monitoring ^b	IMP administration and clinical unit confinement ^c					Out-patient monitoring ^d	EOS
Day	-28 to -1	-3 to -1	0	1 to 3	4 to 7	8	9	10	11	12	13 to 50±2	50±2
FSH (post-menopausal women)	X											
Safety assessments												
Full physical exam	X											X
Abbreviated physical exam			X			X						
Symptom-directed physical exam ^e					X	X	X	X	X	X		
Vital signs ^f	X		X		X	X	X	X	X	X		X
ECG	X		X			X	X	X	X	X		X
Urinalysis	X	X										X
Haem. & Biochem.	X ^g	X			X (D 7 am)	X		X		X		X
Safety serum retention			X									X
Diary card			X	X	X						X	X
AEs & Conmeds.			X	X	X	X	X	X	X	X		X
Study interventions												
Challenge agent inoculation			X									
Pyronaridine administration						X						
Definitive/rescue antimarial treatment											X ^h	
Malaria monitoring and PK blood sampling												
Malaria 18S qPCR ⁱ			X		X	X	X	X	X	X		X
Parasite lifecycle stage qRT-PCR blood sampling											X	
Pyronaridine concentration ^j						X	X	X	X	X		X
Other												
Malaria future research (optional)			X			X					X ^m	X

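### The contraception rule for abstinent women stops at the end of study, 58 days before the protocol's own 100-day post-dose period ends

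*Protocol*

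**What the plan says.** Protocol 5.1, criterion 7, applies to women of childbearing potential "who anticipate being sexually active with a male during the trial must agree to the use of a highly effective method of birth control", combined with a barrier method. The period runs from screening "until 100 days after the last dose of pyronaridine". The criterion explains the 100 days as five half-lives followed by one 30-day menstrual cycle.

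Two notes qualify this.

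- Note a lists the highly effective methods. The list ends with "vasectomised partner, or sexual abstinence or same sex relationship".
- Note b is written for abstinent women. They "must agree to start a double method if they start a sexual relationship with a male during the study". Its next sentence bars planned in vitro fertilisation "within the required contraception period".

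The counterpart for abstinent men, in criterion 9, applies if a relationship begins "during the study and up to 70 days after the last dose of pyronaridine".

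Protocol 4.3 places the single dose on Day 8, and 8.1.8 places the end-of-study (EOS) visit on Day 50±2. Section 4.4 ties a participant's completion to the last visit or procedure in the schedule. Section 8.5.9 follows pregnancies arising in the study and in the 100 days after dosing, and names the two periods separately.

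**The concern.** The protocol fixes a 100-day period after dosing, but the two phrases that decide who must act in it are tied to the trial or study. A woman who is abstinent throughout and does not expect sex with a man during the trial falls outside the opening condition of criterion 7. If she starts a relationship on Day 55, she also falls outside note b. She is nevertheless well inside the period for which the sponsor judged contraception necessary.

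What is at stake is fetal exposure in a rare case, not the statistics. The men's rule includes the post-study extension. The women's rule lacks it, although their required period is longer (100 days against 70).

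**Working it through.** **Inputs**

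- Half-life of about 14 days: Protocol 2.1 and 4.2.
- Contraception period of 100 days after dosing, made up of five half-lives plus a 30-day cycle: criterion 7.
- Dose on Day 8: Protocol 4.3.
- EOS on Day 50, range 48 to 52: Protocol 8.1.8.

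**Reproducing the plan's figure**

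5 × 14 + 30 = 70 + 30 = 100 days, which matches criterion 7.

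**End of the required period**

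Day 8 + 100 = Day 108.

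**End of the participant's study**

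The synopsis counts 8 days from challenge to dosing, 39 days of follow-up after the dose and 3 days after rescue treatment: 8 + 39 + 3 = Day 50. This agrees with the EOS visit.

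**Days without an explicit rule for a woman abstinent through EOS**

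| EOS day | Calculation | Gap |
|---|---|---|
| 48 | 108 − 48 | 60 days |
| 50 | 108 − 50 | 58 days |
| 52 | 108 − 52 | 56 days |

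**What the 58 days consist of**

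Five half-lives end on Day 8 + 70 = Day 78. The stretch from EOS to Day 78 is 78 − 50 = 28 days (26 to 30). The added cycle is 108 − 78 = 30 days. Together, 28 + 30 = 58.

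**Exposure at EOS, for context**

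Section 4.2 says that follow-up after dosing "is equal to three times the elimination half-life of pyronaridine (approximately 14 days". Assuming one-phase elimination at that half-life:

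- at EOS, 42 days after the dose: 0.5^(42/14) = 12.5% remains (0.5^(44/14) = 11.3% to 0.5^(40/14) = 13.8%);
- at Day 78: 0.5^(70/14) = 3.1%;
- at Day 108: 0.5^(100/14) = 0.7%.

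The gap of 58 days does not depend on these percentages.

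**Comparing the two rules for abstinent participants**

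| | Required period ends | Rule for a new relationship runs to | Uncovered days |
|---|---|---|---|
| Men (criterion 9) | Day 8 + 70 = Day 78 | Day 78 | 0 |
| Women (criterion 7, note b) | Day 108 | EOS, Day 50±2 | 58 (56 to 60) |

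**The case against.** The strongest reply is that note a counts abstinence as a highly effective method. On that reading, an abstinent woman falls under criterion 7 with abstinence as her method until Day 108, and if she gives it up she must adopt another listed method with a barrier. This gives note a some effect. The reference in note b to a required contraception period suggests that the authors had the 100 days in mind. The synopsis also states the contraception condition for women of childbearing potential without limiting it to those who expect sexual activity, and 8.5.9 applies its 100-day window to any such woman enrolled.

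This shows that a 100-day reading is possible. It does not supply the missing instruction:

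- The main text of criterion 7 is conditional on expected sexual activity during the trial, and it pairs the method with a barrier. Neither fits an abstinent woman.
- Note b is the specific rule for her, and it stops with the study.
- The contraception-period phrase in note b governs only in vitro fertilisation.
- The synopsis gives no duration.
- Section 8.5.9 treats the study and the 100 days as separate periods, so the first does not contain the second.
- If the study is taken to mean the whole trial, the last participants to finish are still not covered to Day 108.

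Two parts of the objection stand. Participants are instructed through the information sheet and consent form, which were not available, so a gap in practice cannot be shown. The group is also small and could be empty.

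**Conclusion.** The concern holds as a fault in the wording of the criteria. For women abstinent through EOS, 58 days (56 to 60) of the 100-day period carry no explicit obligation, and 28 of those days (26 to 30) fall before five half-lives have passed. The gap rests on a Day 8 dose and on reading the study as ending for each participant at EOS. The split at five half-lives also uses the protocol's 14-day half-life.

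The reach is limited. Women who expect to be sexually active with a man during the trial are expressly bound to Day 108. Those affected are a subset of the women of childbearing potential among at most 18 participants, and the documents do not give their number. No endpoint, estimate or analysis changes. The correction is still worth making, because the rule falls short of a safety period that the sponsor has already set.

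One further fact is secondary and is not part of the conclusion. The schedule's serum test row reads "Serum pregnancy test (all females at screening & WOCBP at EOS", so no scheduled pregnancy test falls after EOS. That is true for every woman in the trial and does not arise from note b.

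**What to change.** In note b, extend the condition for abstinent women so that it covers a relationship begun during the study or within 100 days of the pyronaridine dose, mirroring criterion 9. Bring the opening condition of criterion 7 to the same period. The uncovered time then falls from 58 days to 0.

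The cost is one phrase in each place, plus a matching change to the consent form if it repeats the present text. No visits, samples or analyses are added.

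Optional, and not a correction: criterion 1 requires participants to be contactable until two weeks after EOS, about Day 64 (62 to 66). Extending this to Day 108 for women of childbearing potential (108 − 64 = 44 more days, 42 to 46) and to Day 78 for men (78 − 64 = 14 more days, 12 to 16) would make pregnancies in the 8.5.9 windows more likely to become known. Section 8.5.9 requires reporting once the investigator is aware, not active surveillance, and criterion 13 already collects contact details.

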5.2 EXCLUSION CRITERIA

1. Individual who lives alone, OR, does not satisfy the following criteria: Participants who live alone may be included on a case-by-case basis, following discussion with the Principal Investigator. Participants who live alone must identify and provide contact details of a support person who is aware of the participant's participation in the study and is available to provide assistance if required (for example with contacting the participant in the event that study staff are unable to, or with transporting the participant to and from the study site if required).
2. Known hypersensitivity to pyronaridine, artesunate or any of its derivatives, artemether, lumefantrine or other artemisinin derivatives, proguanil/atovaquone, primaquine, or 4-aminoquinolines.
3. Haematology, biochemistry or urinalysis results at screening or at the eligibility visit that are outside of Sponsor-approved clinically acceptable laboratory ranges (appendix) or are considered clinically significant by the PI or their delegate.
4. Participation in any investigational product trial within the 12 weeks preceding pyronaridine administration.
5. Symptomatic postural hypotension at screening (confirmed on two consecutive readings), irrespective of the decrease in blood pressure, or asymptomatic postural hypotension defined as a decrease in systolic blood pressure ≥ 20 mmHg within 2–3 min when changing from supine to standing position.
6. Any history of anaphylaxis or other severe allergic reactions including face, mouth, or throat swelling or any difficulty breathing, or other food or drug allergy that the Investigator considers may impact on participant safety. Participants with seasonal allergies/hay fever or allergy to animals or house dust mite that are untreated and asymptomatic at the time of dosing can be enrolled in the trial.
7. History of convulsion (including drug or vaccine-induced episodes). A medical history of a single febrile convulsion during childhood (< 5 years) is not an exclusion criterion.
8. Presence of current or suspected serious chronic diseases such as cardiac or autoimmune disease, diabetes, progressive neurological disease, severe malnutrition, hepatic or renal disease. Acute or progressive hepatic or renal disease, porphyria, psoriasis, rheumatoid arthritis, asthma (excluding childhood asthma, or mild asthma with preventative asthma medication required less than monthly), or epilepsy.
9. History of malignancy of any organ system (other than localised basal cell carcinoma of the skin or *in situ* cervical cancer), treated or untreated, within five years of screening, regardless of whether there is evidence of local recurrence or metastases.
10. Individuals with history of schizophrenia, bipolar disorder psychoses, disorders requiring lithium, attempted or planned suicide, or any other severe (disabling) chronic psychiatric diagnosis including generalised anxiety disorder.
11. Individuals who have been hospitalised within five years prior to enrolment for either a psychiatric illness or due to danger to self or others.

12. History of an episode of mild/moderate depression lasting more than 6 months that required pharmacological therapy and/or psychotherapy within the last 5 years; or any episode of major depression.

The Beck Depression Inventory-II (BDI-II) will be used as a validated tool for the assessment of depression at screening. In addition to the conditions listed above, participants with a score of 20 or more on the BDI-II and/or a response of 1, 2 or 3 for item 9 of this inventory (related to suicidal ideation) will not be eligible for participation. These participants will be referred to a general practitioner or medical specialist as appropriate. Participants with a BDI-II score of 17 to 19 may be enrolled at the discretion of an Investigator if they do not have a history of the psychiatric conditions mentioned in this criterion and their mental state is not considered to pose additional risk to the health of the participant or to the execution of the trial and interpretation of the data gathered.

13. History of recurrent headache (e.g. tension-type, cluster, or migraine) with a frequency of ≥ 2 episodes per month on average and severe enough to require medical therapy, during the 2 years preceding screening.

14. Presence of clinically significant infectious disease or fever (e.g., sublingual temperature $\geq 38.5^{\circ}\text{C}$) within the five days prior to inoculation.

15. Blood product donation to any blood bank during the 8 weeks (whole blood) or 4 weeks (plasma and platelets) prior to admission in the clinical unit on Day 8.

16. History or presence of alcohol abuse (alcohol consumption more than 40 g/4 units/4 standard drinks per day), or drug habituation, or any prior intravenous usage of an illicit substance.

17. Any individual who currently (within 14 days prior to inoculation) smokes >5 cigarettes/day.

18. Breastfeeding or lactating; positive serum pregnancy test at screening, positive urine pregnancy test upon admission or at other time points as specified by schedule of activities tables.

19. Any COVID-19 vaccine within 14 days of inoculation, any other vaccination within 28 days of IMP intake, and any vaccination planned up to the final follow-up visit.

20. Any corticosteroids, anti-inflammatory drugs (excluding commonly used over-the-counter anti-inflammatory drugs such as ibuprofen, acetylsalicylic acid, diclofenac), immunomodulators or anticoagulants within the past three months. Any individual currently receiving or having previously received immunosuppressive therapy (including systemic steroids, adrenocorticotropic hormone or inhaled steroids) at a dose or duration potentially associated with hypothalamic-pituitary-adrenal axis suppression within the past year.

21. Use of prescription drugs (excluding contraceptives) or non-prescription drugs or herbal supplements (such as St John's Wort), within 14 days or five half-lives (whichever is longer) prior to inoculation. Limited use of other non-prescription medications or dietary supplements, not believed to affect participant safety or the overall results of the trial, may be permitted on a case-by-case basis following approval by the Sponsor in consultation with the PI. Participants are requested to refrain from taking non-approved concomitant medications from recruitment until the conclusion of the trial.

22. Cardiac/QT risk:

- Family history of sudden death or of congenital prolongation of the QTc interval or known congenital prolongation of the QTc interval or any clinical condition known to prolong the QTc interval.

- History of symptomatic cardiac arrhythmias or with clinically relevant bradycardia.

23. Any history of malaria or participation in a previous malaria challenge trial or malaria vaccine trial.

24. Must not have had malaria exposure that is considered by the PI or their delegate to be significant. This includes but is not limited to: history of having travelled to or lived (>2 weeks) in a malaria-endemic region during the past 12 months or planned travel to a malaria-endemic region during the course of the trial; history of having lived for >1 year in a malaria-endemic region in the past 10 years; history of having ever lived in a malaria-endemic region for more than 10 years inclusive. For endemic regions see <https://malariaatlas.org/explorer/#/>, Bali is not considered a malaria-endemic region.

25. Has evidence of increased cardiovascular disease risk (defined as >10%, 5-year risk for those greater than 35 years of age, as determined by the Australian Absolute Cardiovascular Disease Risk Calculator [<http://www.cvdcheck.org.au/>]). Risk factors include sex, age, systolic blood pressure (mm/Hg), smoking status, total and HDL cholesterol (mmol/L), and reported diabetes status.

26. History of splenectomy.

27. Individual unwilling to defer blood donations to the Blood Service for at least twelve months after the EOS visit.

28. Individual who has ever received a blood transfusion.

29. Any recent (<6 weeks) therapy with an antibiotic or drug with potential antimalarial activity (e.g. chloroquine, piperaquine phosphate, benzodiazepine, flunarizine, fluoxetine, tetracycline, azithromycin, clindamycin, doxycycline etc.).

General conditions

30. Any individual who, in the judgement of an Investigator, is likely to be non-compliant during the trial, or is unable to cooperate because of a language problem or poor mental development.

31. Any individual in the exclusion period of a previous trial according to applicable regulations.

32. Any individual who is an Investigator, research assistant, pharmacist, trial coordinator, or other staff thereof, directly involved in conducting the trial.

33. Any individual without good peripheral venous access.

Biological status

34. Positive result on any of the following tests: hepatitis B surface antigen (HBs Ag), anti-hepatitis B core antibodies (anti-HBc Ab), anti-hepatitis C virus (anti-HCV) antibodies, anti-human immunodeficiency virus 1 and 2 antibodies (anti-HIV1 and anti-HIV2 Ab).

35. Positive urine drug test. Any drug listed in the urine drug screen unless there is an explanation acceptable to an Investigator (e.g., the participant has stated in advance that they consumed a prescription or over-the-counter product that contained the detected drug) and the participant has a negative urine drug screen on retest by the pathology laboratory.

36. Severe G6PD deficiency.

37. Positive alcohol breath test.

38. Positive for SARS-CoV-2 by PCR or RAT.

39. Positive for red cell antibodies

